Most recently, the use of esophageal VCE in the ED was compared with the validated triage system, the Glasgow-Blatchford Score, to identify the number of patients who may be suitable for outpatient care [8]. Patients who presented to the ED for suspected acute UGIB were enrolled and administered esophageal VCE. For capsules that passed the pylorus and reached the duodenum, high-risk lesions were detected with a 95% sensitivity (95% CI: 72%-100%) and a 92% specificity (95% CI: 73%- 99%) compared with the Blatchford Score that demonstrated a 94% sensitivity (95% CI: 72%-100%) and a 16% specificity (95% CI: 5%-37%).

There has been one feasibility study published to test whether VCE can reduce hospital admissions in patients with suspected UGIB. In a prospective randomized controlled trial in which patients who presented with symptoms or signs suggestive of UGIB were randomized to receive either the standard treatment of hospital management versus VCE. Patients were also graded by Glasgow Blatchford score (GBS) at the ED for assessment of need of hospital admission. In this study, seventy-one patients fulfilled the recruitment criteria, with 37 subjects randomized to the VCE group and 34 subjects randomized to standard group. Seven VCE patients with active bleeding or significant endoscopic findings were admitted to the hospital compared with the standard group in which all 34 patients were admitted. There was no difference in the clinical outcome in terms of recurrent bleeding and 30-day mortality. In addition, hospital admission was also greatly reduced if VCE results were used instead of the GBS to determine whether patients were admitted or managed in the outpatient setting.[9]

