## **2.2 Rationale**

We believe there is an opportunity to improve the risk stratification of acute UGIB that presents to the Emergency Department through the use of Video Capsule Endoscopy. Our primary hypothesis is that VCE allows for safe outpatient management of ED patients with suspected upper GI hemorrhage. A multicenter randomized control trial is proposed to investigate the safety of this diagnostic modality.

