**Other Outcomes:**

1. Patient satisfaction with the VCE procedure. (Form Used: *CHEER #4*)

2. GI Physician Final Read and Site physician agreement of VCE results. (Form Used: *CHEER #5*)
3. Serious Adverse Events at Day 7 and Day 30 (Mortality, Re-Bleeding, Total Blood Transfusions, Surgery, Capsule-specific). (Form Used: *CHEER #7*)
4. ED Length of Stay (hours).
5. Hospital Length of Stay (days).
6. Cost-effective analysis.
  - At conclusion of study, we will construct a model using standard decision analysis software to examine the cost-effectiveness of three available strategies for a base-case patient who presents to the ED with either mild or moderate risk scenarios (by Glasgow-Blatchford Score) for requiring invasive hemostatic intervention (i.e., endoscopic, surgical, etc.) The three available diagnostic strategies are (1) direct imaging with video capsule endoscopy performed in the ED, (2) risk stratification using the Glasgow-Blatchford score, and, finally, (3) an admit-all strategy.

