**4.4 Study procedure:**

1. Screen potential patients with signs of upper GI bleeding (melena, h/o hematemesis or coffee-ground emesis) from general pool of ED patients. (Form used, *CHEER:1*)
2. Patients who screen as eligible will be approached about potential interest, to review of inclusion and exclusion criteria, and obtain informed consent. (*See below for full list of inclusion/ exclusion criteria.*)
3. Research Coordinator will calculate traditional risk stratification scores (Glasgow – Blatchford and Rockall).
4. All consented patients will be given a study ID and recorded in enrollment log. (Form used, *CHEER:2*)
5. Once enrolled, all subjects will be randomized to either Active Control (AC) [admission plus EGD within hospital stay] or experimental Capsule Endoscopy Risk Assessment (CERA) in ED.
6. Only patients randomized to the experimental arm will receive video capsule endoscopy in the emergency department. 20 to 60 minutes before capsule ingestion, each patient in the experimental arm receives a single dose of intravenous metoclopramide 10 mg (or erythromycin 500mg intravenously if there is a contraindication), which helps to promote gastric motility and improves visualization of the gastric mucosa at endoscopy. The Research Coordinator (RC) will prepare the patient for VCE. (*See below for description of procedure.*)
7. Within 2 hours of presenting to the ED, patient will ingest video capsule-- RC will monitor progress on real-time viewer for passage through pylorus. Upon passing the pylorus, we will record 5 more minutes of video or until battery runs out – whichever occurs first.
8. Patient data will be completed using a standardized data collection tool including the following elements: chief complaint of patient, history of present illness, past medical history, pertinent lab findings, current medications, vital signs, focused physical exam findings and all relevant treatments administered during the ED and hospital stay. (Form Used, *CHEER:3*)

9. At completion of VCE, patient satisfaction regarding VCE will be assessed in patients in the experimental group. (Form used, *CHEER*: 4)
10. For Active Control (AC) group each patient will be admitted.

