### **11.2 Sample Size Considerations**

With 100 patients, we will have adequate power (i.e.  $\geq 80\%$ ) to detect a 25% difference or greater in admission rates for subjects with low risk lesions with p- value less than 0.05. We assume that the controls will a 100% admission rate. We anticipate 20% or less of all subjects to be diagnosed with a high-risk lesion, we are unlikely to have adequate power to detect a significant difference in the hospital admission rate between the two study groups.

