### **11.3 Final Analysis Plan**

The analysis will be conducted in several stages. First, we will compare the baseline characteristics of the two study groups to determine if randomization was successful. We will also compare the baseline characteristics of the study samples by enrollment site. Second, we will compare the VCE and EGD results and classify all study subjects according to whether there is a high versus low risk lesion present. The VCE and EGD results may differ because they are not being performed at the same time and GI bleeds can resolve or change so it is unlikely that there will be perfect agreement between the two modalities. In cases where one modality identifies a low risk lesion and the other one a high-risk lesion, we will classify the lesion as high risk. If the VCE could not adequately visualize the tract, we will classify the results according to the EGD. We will compare the sensitivity and specificity of VCE and EGD for identifying high risk lesions. Finally, we will separately compare the admission rates of high-risk lesions and low risk lesions between the two study groups. We will compare admission rates aggregated across the four study centers as well as within each study center.

For tertiary outcomes, we will compare the outcomes by study group using a chi-square test statistic if the outcome is categorical such as the presence of an adverse event and a t test (normally distributed) or median test (non-normally distributed) if the outcome is continuous such as hospital or ED length of stay.

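### Safe outpatient management is the primary hypothesis, but categorical clinical harm is compared between arms only by a chi-square difference test with no interval or bound, which cannot support a claim of safety

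*Combined protocol and SAP*

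**What the plan says.** Section 2.2 states: "Our primary hypothesis is that VCE allows for safe outpatient management of ED patients with suspected upper GI hemorrhage". It adds that the trial is proposed to investigate the safety of the modality. Sections 3.1 and 7.3.1 likewise put safe discharge into the primary goal.

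The rest of the plan is built on admissions. The primary outcome in 3.2.1 is the percentage discharged home, the hypotheses in 11.1 concern admission rates by lesion risk, and 11.2 sizes the trial "to detect a 25% difference or greater in admission rates for subjects with low risk lesions with p- value less than 0.05".

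The clinical harms appear under Other Outcomes in 3.2: "Serious Adverse Events at Day 7 and Day 30 (Mortality, Re-Bleeding, Total Blood Transfusions, Surgery, Capsule-specific". Section 11.3 treats outcomes of this kind as tertiary: "we will compare the outcomes by study group using a chi-square test statistic if the outcome is categorical such as the presence of an adverse" (sentence cut short here), with a t test or median test for continuous outcomes. No confidence interval, margin, acceptable excess or expected event rate is given for them. Section 11.3 also compares admission rates between arms among subjects with high-risk lesions.

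**The concern.** A difference test is built to detect a difference. A small p-value shows harm (or benefit). A large one shows only that the data did not settle the question, and a small trial makes that outcome likely. If 11.3 supplies the clinical evidence for the hypothesis in 2.2, the only test result compatible with that hypothesis is a non-significant one, so a smaller trial would find it easier to appear safe.

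The primary outcome does not fill the gap, because the percentage discharged rises with every discharge, safe or not. The high-risk-lesion admission comparison does bear on safety, but it has no bound either. Section 11.2 appears to concede that it is underpowered, since 20% or fewer of subjects are expected to have such a lesion. Section 11.2 says nothing about power for death, re-bleeding, transfusion or surgery.

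At stake is whether the final report could call discharge after capsule endoscopy safe when the data are compatible with a substantial excess of serious outcomes.

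**Working it through.** **Inputs.** From 11.2: 100 patients, p < 0.05, high-risk share 20% or less, and "We assume that the controls will a 100% admission rate". Assumed because the documents do not say: 1:1 allocation (50 per arm), a two-sided test, complete follow-up, and control event rates from 0% to 10%.

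**1. The plan's own figure.** Low-risk subjects: 100 × 0.80 / 2 = 40 per arm. For 100% v 75%, the pooled rate is 0.875 and

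z = [0.25√40 − 1.96√(2 × 0.875 × 0.125)] / √(0.75 × 0.25) = (1.581 − 0.917) / 0.433 = 1.53,

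which gives power of about 94%. The stated 80% or more holds, but it is power for admissions, not for harm.

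**2. Chance of missing a true 10-point excess.** With x control events and y capsule-arm (CERA) events out of 50 each, and control rate c:

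miss = 1 − Σ Bin(y; 50, c + 0.10) × Bin(x; 50, c), summed over tables with p < 0.05 and y > x.

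| Control v CERA | Uncorrected chi-square | Fisher |
|---|---|---|
| 0% v 10% | 25% | 62% |
| 1% v 11% | 40% | 65% |
| 2% v 12% | 49% | 69% |
| 3% v 13% | 54% | 72% |
| 5% v 15% | 61% | 76% |
| 10% v 20% | 70% | 81% |

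The first row can be checked by hand. With x = 0 the statistic is 100y/(100 − y), which passes 3.84 from y = 4, so the miss rate is P(Bin(50, 0.10) ≤ 3) = 25%. Fisher needs y = 6 (0 v 5 gives p = 0.056), and P(Bin(50, 0.10) ≤ 5) = 62%.

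Expected events per cell are 50(c + 0.05), which is below 5 when c is below 5%. In that range the uncorrected chi-square is itself unreliable. For 5-point excesses (2% v 7%, 5% v 10%, 10% v 15%) the miss rate is 80% to 88% by chi-square and about 94% by Fisher.

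**3. One non-significant result.** Control 2 v CERA 7: chi-square = 100 × 5² / (9 × 91) = 3.05, p = 0.08. The Wilson limits are 1.10% to 13.46% (control) and 6.95% to 26.19% (CERA). The Newcombe limits for the excess, in points, are:

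- lower: 10 − √[(14 − 6.95)² + (13.46 − 4)²] = −1.8
- upper: 10 + √[(26.19 − 14)² + (4 − 1.10)²] = +22.5

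**4. What few events would leave open.** Newcombe upper limits at 50 per arm, same formula:

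| CERA v control events | Upper limit (points) |
|---|---|
| 0 v 1 | +5.3 |
| 0 v 0 | +7.1 |
| 1 v 1 | +8.7 |
| 2 v 2 | +9.9 |
| 2 v 1 | +11.6 |

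For example, 2 v 1: 2 + √[(13.46 − 4)² + (2 − 0.35)²] = 11.6. If both arms truly have the same rate of 2% to 4%, the upper limit falls below 10 points in only 65% (at 2%) to 56% (at 4%) of trials.

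**5. The high-risk-lesion comparison.** At most 100 × 0.20 / 2 = 10 per arm. Even 100% v 75% admission would then have exact power of 22% (chi-square) or 8% (Fisher).

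**The case against.** The best defence is that nothing in the plan says a non-significant adverse-event test will be read as proof of safety. Section 11.1 has no adverse-event hypothesis, 11.3 calls these outcomes tertiary, and the primary outcome is discharge. In a 100-patient trial, a descriptive tertiary test is ordinary. This stands in part. A reader might infer from the account of the earlier randomised study in 2.1, "There was no difference in the clinical outcome in terms of recurrent bleeding and 30-day mortality", that the team will read its own data in the same way. That sentence reports someone else's result and is not a decision rule for this trial. But the tertiary label does not answer 2.2, 3.1 and 7.3.1, which rest the primary claim on safety. Nor does monitoring by the board in section 12, which has no numerical rule and does not govern what the final report may conclude.

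Three stronger readings are tempting but not supported:

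- A reader might infer that a 10-point harm would usually be missed. For the test named in 11.3, that is true only from a control rate of about 3%. It is a coin-flip at 2% and false at 0% to 1%. The documents give no event rate, and by excluding unstable and high-score patients they leave a low one possible.
- A reader might infer that chi-square is the only between-arm safety analysis. The high-risk-lesion admission comparison also bears on safety, and total transfusions, if analysed as a count, could get a t or median test. Neither has a bound.
- A reader might infer from the tied counts that 9 to 10 points is the smallest excess the trial can exclude. Those limits belong to exact ties of 1 v 1 and 2 v 2. Other counts give smaller or larger limits.

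**Conclusion.** The point holds as a mismatch between claim and analysis. Safety is the primary hypothesis in 2.2, and the planned analysis of categorical clinical harm cannot support it. The size depends on the control rate: a true 10-point excess goes undetected in 25% to 70% of trials by uncorrected chi-square over control rates of 0% to 10%, and in 62% to 81% by Fisher. These figures assume 50 per arm, two-sided 0.05 and complete follow-up. Different allocation or losses would change them. The logical defect rests on none of these assumptions, because no p-value from a difference test bounds the excess. The change should be made. It is a correction to analysis and reporting and does not mean that the trial's admission result is unsound.

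**What to change.** **Section 11.3.** For each Day 7 and Day 30 serious outcome that both arms can have, report the CERA minus Active Control risk difference by randomised arm, with a two-sided 95% Newcombe or Miettinen-Nurminen interval. Base any safety statement on the upper limit. State that p > 0.05 will not be reported as evidence of safety or of no difference. The restriction to outcomes both arms can have matters because capsule-specific events cannot occur in controls, and because the serious-event definition in 10.2 includes initial hospitalisation while every control is admitted by design.

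**Section 11.2.** State that the trial is not sized to exclude a clinically important excess of serious outcomes. Illustrate with upper limits at 50 per arm for example counts (CERA v control): 0 v 0, +7.1 points; 1 v 1, +8.7; 2 v 2, +9.9; 2 v 1, +11.6. Label these as illustrations, not as a smallest excludable excess.

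**Sections 2.2, 3.1 and 7.3.1.** Reconcile their safety wording with the discharge outcome in 3.2.1 and the admission hypotheses in 11.1.

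**Cost.** Plan wording and a few lines of analysis code, with no new patients or data. The downside is a more modest safety conclusion, because the report must say which excess it can and cannot exclude. A combined harm endpoint is optional and is not needed for this correction.

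### The median test planned for skewed length of stay in 11.3 is inefficient; a prespecified Wilcoxon rank-sum test usually has more power, but it tests a different hypothesis

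*Combined protocol and SAP*

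**What the plan says.** Section 11.3 introduces these comparisons with "For tertiary outcomes, we will compare the outcomes by study group". It plans a chi-square test for categorical outcomes and, for continuous ones, "a t test (normally distributed) or median test (non-normally distributed) if the outcome is continuous such as hospital or ED length of stay". It does not say how normality will be judged, or whether the median test is uncorrected, continuity-corrected or Fisher's.

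Section 3.2 lists ED stay (in hours) and hospital stay (in days) among six other outcomes. It does not say how hospital stay is scored for a subject sent home from the ED.

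The only power statement, in section 11.2, concerns admission: "With 100 patients, we will have adequate power" to "detect a 25% difference or greater in admission rates for subjects with low risk lesions with p- value less than 0.05". No effect size, SD or power is given for length of stay. Section 4.4 says that subjects are randomized to the two arms but states no ratio.

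**The concern.** Length of stay is normally right-skewed, so the non-normal branch is the one likely to be used. The median test keeps only which side of the pooled median each subject falls on and discards how far from it. For normal data on the log scale, its asymptotic efficiency relative to the t test is 2/π and that of rank-sum is 3/π. The ratio is 2/3, so 100 subjects analysed by the median test carry about the information of 67 analysed by rank-sum.

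The test is also coarse in a trial of this size. Its real type I error depends on details that the plan leaves open, including a version that could be chosen after the data are seen. At stake is a real difference in ED or hospital stay that goes undetected, or a tertiary p-value whose level is not known in advance.

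**Working it through.** **Inputs.** Total of 100 and a level of 0.05 (section 11.2); two-sided testing is assumed. The 50 per arm is an assumption. Every length-of-stay distribution below is also an assumption; the 4-day scale for the zero-day scenarios is the background median in section 2.1.

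**The plan's own figure.** Section 11.2 says "We assume that the controls will a 100% admission rate" and expects at most 20% high-risk lesions, which leaves about 80 low-risk subjects, or 40 per arm if 1:1. For 100% v 75% admission the pooled proportion is 0.875.
- SE under the null = √(2 × 0.875 × 0.125/40) = 0.0740.
- SE under the alternative = √(0.75 × 0.25/40) = 0.0685.
- z = (0.25 − 1.96 × 0.0740)/0.0685 = 1.53, so power is about 93.8%.

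The stated lower bound of 80% holds. It says nothing about length of stay.

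**Type I error of the median test, no ties.** Let a be the number above the pooled median in one arm. Under the null, a is hypergeometric.
- 50 v 50, uncorrected: χ² = 0.16(a − 25)². A deviation of 4 gives 2.56 and 5 gives 4.00, against the critical value 3.84. Size = P(|a − 25| ≥ 5) = 7.1%.
- 50 v 50, continuity-corrected: χ² = 0.16(|a − 25| − 0.5)². A deviation of 5 gives 3.24 and 6 gives 4.84. Size = P(|a − 25| ≥ 6) = 2.7%. Fisher's version gives the same.
- 49 v 51: both versions first reject at |a − 24.5| = 5.5. Size = 4.5%.
- 48 v 52: 7.1% uncorrected, 2.7% corrected. 49 v 49: 4.3% for both.
- Averaged over simple randomization of 100: 5.7% and 3.5%.

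With whole-day ties (simulated), the size is about 5–6% uncorrected and 3–3.5% corrected. Rank-sum has an exact size of 4.95% at 50 v 50 without ties, and about 5% in simulation with ties.

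**Power, 20,000 simulated trials per scenario, 50 per arm unless stated.**

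| Assumed scenario | Median, uncorrected | Median, corrected | Rank-sum |
|---|---|---|---|
| Log-normal shift 0.5, log-SD 1.0 | 58% | 41% | 68% |
| Same, at 49 v 51 | about 49% | about 49% | 67% |
| Whole days, medians 3.0 v 2.3, log-SD 0.6 | 40% | 32% | 54% |
| Exponential, ratio 2 | 72% | 57% | 83% |
| 25% zero-day stays, capsule arm only, otherwise continuous | 36% | 22% | 59% |
| Same, whole days | 26% | 20% | 59% |
| 50% zero-day stays, otherwise continuous | 94% | 87% | 99% |
| 81% zero-day stays | about 100% | about 100% | about 100% |
| Log-Laplace shift 0.5 | 66% | 49% | 56% |
| Log-Cauchy shift 1.0 | 88% | 78% | 73% |

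The 49 v 51 row is the cleanest comparison, because both tests are then near their nominal level. The gap widens there from 10 to about 18 points, so part of the 58% at 50 v 50 comes from the inflated level.

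**Equal medians, unequal shapes.** Rejection rates in the same column order: an ED-stay mixture against a log-normal, 9%, 4% and 33%; hospital stay with 40% zeros against a log-normal, 10%, 5% and 16%. Over all such scenarios tried, rank-sum rejected in 7–33%.

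**The case against.** The median test is a recognised method, and three stronger readings that a reader might infer do not stand.

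*That the median test misses its 5% level in this trial.* The 7.1% and 2.7% figures need 50 v 50, or a near-identical split such as 48 v 52, and no ties. The documents give no ratio, one subject's imbalance brings the size to 4.5%, and hospital stay in days will be tied. What stands is that the level cannot be known in advance while the version is unnamed.

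*That rank-sum costs nothing.* It tests whether stays tend to be longer in one arm. The design invites different shapes: only the capsule arm is observed for at least four hours after ingestion, and only that arm is sent home from the ED by protocol (section 4.4). If the question is strictly about medians, rank-sum can reject when they are equal, and more often than the median test in the two scenarios shown. This objection stands and has to be disclosed. Those rejections do reflect real differences between the distributions, and the uncorrected median test is itself off its level there.

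*That length of stay is the main resource outcome and drives the cost result.* Section 11.3 calls such outcomes tertiary, and section 11.4 ties cost to fewer admissions, not to days or to any length-of-stay p-value.

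The power gain also has limits. Very heavy tails can favour the median test. In the feasibility trial cited in section 2.1, 30 of 37 capsule patients (81%) were not admitted; at that rate either test detects the difference in hospital stay. That does not settle ED stay, or a smaller discharge effect such as the 25 points in section 11.2.

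**Conclusion.** The concern holds as a point about efficiency and specification. For typical skewed stays the planned test gives up roughly 10 to 30 percentage points of power against rank-sum, depending on the version and scenario, and more in some zero-day cases. Its true level ranges from about 3% to 7% depending on matters that the plan does not fix. These sizes rest on assumed distributions and mostly on an assumed 50 per arm, since the documents supply neither. The direction is reliable for log-normal, exponential and partly zero stays. It is not reliable for very heavy tails, and the gain disappears when about 80% of capsule stays are zero. The outcomes are tertiary, so this is a minor improvement.

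**What to change.** In section 11.3:

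1. Replace the median test with the Wilcoxon rank-sum test, named in advance for ED and hospital length of stay and not chosen after a normality check.
2. State that it tests whether stays tend to be longer in one arm, not whether the medians are equal.
3. Report the probability index P(X > Y) with a 95% CI, beside the median in each arm. A Hodges-Lehmann shift is hard to interpret with many zeros: with 25% zero-day capsule stays and otherwise equal whole-day stays, it came to about 1.1 days in simulation against a median difference of about 0.7.
4. Score hospital stay as 0 days for subjects discharged from the ED, so that all randomized subjects are compared and not only those admitted.

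The cost is a few sentences, with no new data or patients. The downside is that equality of medians is no longer the hypothesis tested.

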#### 3.2 Study Outcome Measures

3.2.1 Primary Outcome: (1) Percent Discharged Home. Assumption is that 100% of Active Control (AC) group will be admitted.

3.2.2 Secondary Outcome: Sensitivity and specificity of VCE compared to EGD. *Endpoints will be defined in the following way:*

Positive Video Capsule Endoscopy will be defined as:

1. Fresh blood or evidence of active bleeding visualized in upper GI tract.
2. Coffee ground blood visualized in upper GI tract, but no active bleeding seen.
3. A High Grade Non-Variceal Lesion (Forrest Ia, Ib, IIa or IIb).
4. Signs of Variceal Hemorrhage.
5. Signs of malignancy visualized in upper GI tract.

Negative VCE:

5. Clean stomach and duodenum, no fresh blood or coffee ground.
6. Upper GI pathology non-causative/ incidental.
7. A low grade non-Variceal lesion (Forrest IIc, III).

An Inconclusive VCE:

8. Any capsule that does not pass the pylorus before battery life is expired (and does not detect lesion in stomach or esophagus).

Positive EGD

1. Fresh blood or evidence of active bleeding.
2. Coffee ground but no active bleeding seen.
3. A High Grade Non-Variceal Lesion (Forrest Ia, Ib, IIa or IIb).
4. Signs of Variceal Hemorrhage.

Negative EGD

5. Clean stomach and duodenum, no fresh blood or coffee ground.
6. Upper GI pathology non-causative/ incidental.
7. A low grade non-variceal lesion (Forrest IIc, III).

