During hospital admission, EGD will be performed on all subjects and hemostasis therapy applied as necessary. The study team decided against mandating that EGD be performed within 24 hours of hospital admission. This is a pragmatic trial. The longer the duration between the inpatient EGD and the ED VCE the greater the likelihood of discrepancy in the findings that may be due to a change in the lesion as part of its natural course or due to treatments delivered. However, the primary objective of the study is not to evaluate diagnostic accuracy of the ED VCE. The study team decided it was more important to enroll subjects in a timely manner than exclude subjects because the inpatient EGD was not completed within 24 hours.

For the experimental CERA group, subjects will be monitored for a minimum of 4 hours after ingestion. VCE will be undergo a formal review after completion of the VCE by a staff gastroenterologist with extensive experience in VCEs of the small bowel, colon, and esophagus. Both research personnel and the gastroenterologist will undergo a capsule training program organized by Medtronic and receive accreditation after the training.

11. Subjects in the experimental arm who have no sign of active bleeding, show no serious endoscopic findings on capsule, and have stable hemoglobin, blood pressure and heart rate for at least 4 hours will be discharged from the ED. Discharged CE patients will be scheduled to have an outpatient EGD within 3 days post discharge. Patients will be instructed to return to the ED sooner if signs of new bleeding develops. The Research Coordinator will facilitate setting up this appointment for the patient.

Any subject in the experimental arm with a positive VCE or a negative VCE but has a drop in Hemoglobin  $\geq 3$  at 4 hours or an elevated HR or low BP will be admitted. A hemoglobin drop between 2 and 3 will NOT automatically transfer patient to active control arm. In these cases, decision to proceed will be up to discretion of treating physician. We anticipate that all admitted patients in the experimental arm will undergo EGD in the hospital (same as AC arm.)

12. Primary Outcome: (1) Percent Discharged Home. Assumption is that 100% of Active Control / standard risk assessment will be admitted.
13. Secondary Outcome: Sensitivity and specificity of VCE compared to EGD

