### **8.8 Cheer 8: Hospitalization Course/ Chart Review**

This form collects information on the hospitalization and procedures during the patient's hospital stay.

**8.9      Cheer 9: Adverse Event Form/ Serious Event  
From**

This form is completed if patient reports any AE or SAE's. Report to PI within 24 hours, SAE's are reported immediately.

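### Sections 3.2 and 11.3 compare hospital length of stay by arm without saying how subjects discharged from the ED are counted; if they are left out, a true saving can be hidden or reversed

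*Combined protocol and SAP*

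**What the plan says.** Section 3.2 lists ED length of stay (hours) and hospital length of stay (days) as separate items under Other Outcomes. Section 11.3 gives the method for tertiary outcomes: "we will compare the outcomes by study group using a chi-square test statistic if the outcome is categorical", and a t test or median test "if the outcome is continuous such as hospital or ED length of stay". No section gives the start and end of the hospital stay, its analysis population, or its value for a subject who is never admitted.

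Whether a subject has an inpatient stay depends on the arm:

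- **Controls.** Section 3.2: "Assumption is that 100% of Active Control (AC) group will be admitted".
- **CERA, reassuring capsule and stable values.** Section 4.4, step 11: these subjects "will be discharged from the ED. Discharged CE patients will be scheduled to have an outpatient EGD within 3 days post discharge".
- **CERA, otherwise.** The same step admits "Any subject in the experimental arm with a positive VCE or a negative VCE but has a drop in Hemoglobin" of the stated size, or with abnormal heart rate or blood pressure.

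Section 8.8 describes the chart-review form thus: "This form collects information on the hospitalization and procedures during the patient's hospital stay". The form in Appendix 18.13 has a hospital discharge date. It shows no admission date and no entry for not admitted or 0 days.

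**The concern.** Having an inpatient stay is an event after randomisation. In the control arm everyone is assumed to have one. In the CERA arm it is decided by capsule findings and stability, that is, by severity. An analyst who finds the field empty for a CERA subject sent home could well treat that subject as missing. The test would then compare the more severe CERA subjects with controls of every severity, and the balance given by randomisation would be lost.

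Another analyst could enter 0 days for the same subjects and stay within Section 11.3. The two could report opposite directions from the same data. At stake is what the trial says about hospital time, which is the natural companion to the percentage discharged home.

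**Working it through.** **The plan's own figures.** The plan gives no figure for length of stay. Its one power statement (Section 11.2) is at least 80% power for a 25-point difference in admission among low-risk subjects, with controls at 100%. With 1:1 allocation (assumed) and 20% high-risk, 40 low-risk subjects per arm remain. Power for 100% against 75% is then 93.8% (pooled normal approximation, two-sided 0.05), so the statement holds. It matters here only because it makes 75% low-risk CERA admission a scenario of the plan's own.

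**Inputs**

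- h, share high-risk: 20%, the upper figure in Section 11.2.
- a, share of low-risk CERA subjects admitted: 0% to 75%.
- All controls and all high-risk CERA subjects admitted: the first is the plan's assumption, the second is mine.
- LH and LL, mean stay of high- and low-risk subjects: 4 and 2 days, assumed. The only stay figure in the documents is a median of 4.0 days in inpatients who had EGD (Section 2.1), not split by risk.

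**Formulas**

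- Control mean = h·LH + (1−h)·LL = 0.2×4 + 0.8×2 = 2.4 days.
- CERA share admitted: q = h + (1−h)·a.
- CERA mean, all randomised, 0 if sent home: h·LH + (1−h)·a·LL.
- CERA mean, admitted only: the previous line divided by q.

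| a | q | CERA admitted only | Difference from control | CERA all randomised | Difference from control |
|---|---|---|---|---|---|
| 0% | 20% | 0.8/0.2 = 4.0 | +1.6 | 0.8 | −1.6 |
| 25% | 40% | 1.2/0.4 = 3.0 | +0.6 | 1.2 | −1.2 |
| 50% | 60% | 1.6/0.6 = 2.67 | +0.27 | 1.6 | −0.8 |
| 75% | 80% | 2.0/0.8 = 2.5 | +0.1 | 2.0 | −0.4 |

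**Why the sign turns.** The admitted-only difference equals (LH−LL)·(h/q − h). It is positive whenever high-risk stays are longer and some CERA subjects go home (q below 1). The all-randomised difference equals −(1−h)·(1−a)·LL, which is negative whenever some low-risk CERA subjects go home. In the last row the admitted-only result looks close to zero, but it is 0.1 − (−0.4) = 0.5 day away from the all-randomised effect.

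**Equal stays.** With LH = LL = 3 days, the control mean and the admitted-only CERA mean are both 3.0. The all-randomised CERA mean runs from 0.6 (a = 0%) to 2.4 (a = 75%). There is no reversal, but the whole saving is hidden.

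**Fewer high-risk subjects.** With h = 10% and stays of 4 and 2 days, the control mean is 2.2. Admitted-only CERA is 4.0 at a = 0% and 2.26 at a = 75%; all-randomised CERA is 0.4 and 1.75.

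**How often a test would mislead.** I simulated 1,000 trials per scenario with h = 20%, 50 per arm, lognormal stays with coefficient of variation 0.8 (assumed), and a Welch t test. With stays of 4 and 2 days, the admitted-only test was significant in the wrong direction in about 25%, 10%, 4% and 2% of trials for a = 0%, 25%, 50% and 75%. With 5 and 2 days and a = 0% the figure was 41% (median test 46%). With 4 and 3 days it was about 2% to 4%. With everyone included and stays of 4 and 2 days, the t test found the shorter CERA stay in about 93%, 78%, 49% and 15%.

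**The case against.** The strongest reply is that the plan never states an admitted-only test. Section 11.3 says only that outcomes are compared by study group, and entering 0 days for a subject sent home fits that wording and gives the right direction. This stands. The point is that the text permits both analyses, not that it prescribes the wrong one. The chart-review form does not settle it either: nothing says the form is skipped for subjects discharged from the ED, and its disposition list includes home.

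It is also fair that the stay lengths are assumptions, that reversal needs longer stays in high-risk subjects, and that a significant wrong-direction result was a minority event in every scenario run. Loss of the saving, however, does not need unequal stays.

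A reader might infer three stronger things that the documents do not support:

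- **That admitted CERA subjects will be a minority.** The cited feasibility trial suggests so (7 of 37, or 19%, against 34 of 34 controls). In the plan's own 25-point scenario, however, 80% of the CERA arm is admitted.
- **That length of stay feeds the cost analysis.** Section 11.4 links savings to fewer admissions, and Section 3.2 describes a decision model for a base-case patient. Neither names trial length of stay as an input.
- **That ED length of stay is biased because CERA "subjects will be monitored for a minimum of 4 hours after ingestion".** Every randomised subject has an ED stay. If the monitoring lengthens it, that is a real consequence of the strategy and can properly be compared by arm.

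**Conclusion.** The concern holds as a gap in definition. Sections 3.2 and 11.3 leave hospital length of stay undefined for subjects discharged from the ED, and one natural way of filling the gap gives a severity-selected comparison in one arm only. Under the assumed 4- and 2-day stays and 20% high-risk, that comparison shows CERA 0.1 to 1.6 days longer, when over all randomised subjects it is 0.4 to 1.6 days shorter. With equal stays it shows no difference at all.

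The result rests on the assumed stay lengths and on admission of all high-risk CERA subjects; the test frequencies also rest on 50 per arm and the assumed spread. The outcome is tertiary, so the primary conclusion on the percentage discharged home is unaffected. The change should still be made, because it decides what the trial can say about hospital time.

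**What to change.** In Sections 3.2 and 11.3, define hospital stay for all randomised subjects, analysed by assigned arm, with 0 hospital days for anyone discharged from the ED. Total time from ED arrival to final departure from the index visit is an acceptable alternative. Choose one before the data are examined, and state its start and end points.

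Because of the zeros, report the mean difference with a bootstrap or permutation interval in place of the choice between t test and median test. When more than half the CERA arm goes home, its median is 0 however long the others stay, so a median says little about days saved. Label stay among admitted subjects as descriptive only. ED length of stay can remain a by-arm comparison.

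The cost is a few sentences of plan text and some abstraction. For the index stay, the forms shown record only a hospital discharge date, so arrival, admission and departure times must be taken from the medical record. No new patient procedure is needed. Precision may be modest: with 75% of low-risk CERA subjects admitted, the all-randomised t test detected the shorter stay in only about 15% of simulated trials.
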